4.5 Adverse Events

4.5.1 Definitions

Adverse Event

Any untoward medical occurrence in a patient or clinical trial patient administered a medicinal product and which does not necessarily have a causal relationship with this treatment.

Comment: An AE can therefore be any unfavourable and unintended sign (including an abnormal laboratory finding), symptom, or disease temporally associated with the use of an investigational medicinal product (IMP), whether or not considered related to the IMP.

Adverse Reaction

All untoward and unintended responses to an IMP related to any dose administered.

Comment: All AEs judged by either the reporting Investigator or the Sponsor as having a reasonable causal relationship to a medicinal product qualify as adverse reactions. The expression reasonable causal relationship means to convey in general that there is evidence or argument to suggest a causal relationship.

Unexpected Adverse Reaction

An adverse reaction, the nature or severity of which is not consistent with the applicable product information (e.g. Investigator's Brochure for an unauthorized IMP or SmPC for an authorized product).

Comments: When the outcome of an adverse reaction in this study is not consistent with the applicable product information, i.e. Section 4.8 of the SmPC, this adverse reaction should be considered as unexpected.

Serious Adverse Event

Any untoward medicinal occurrence or effect that at any dose:

- Results in death
- Is life-threatening
- Requires hospitalization or prolongation of existing hospitalization
- Results in persistent or significant disability or incapacity
- Is a congenital anomaly or birth defect

Comments: Life-threatening in the definition of a serious adverse event (SAE) or serious adverse reaction refers to an event in which the patient was at risk of death at the time of event; it does not refer to an event which hypothetically might have caused death if it was more severe.

Medical judgment should be exercised in deciding whether an AE/reaction is serious in other situations. Important AEs/reactions that are not immediately life-threatening or do not result in

[figure not shown]
death or hospitalization but may jeopardize the patient or may require intervention to prevent one of the other outcomes listed in the definition above, should also be considered serious.

4.5.2 Occurrence of Selected Adverse Events (Including Serious Adverse Events) – Main Categories

AEs considered clinically relevant are listed in Table 2. Any of these AEs that have occurred during the time between the 3-year follow-up visit and the 5 to 7-year follow-up visit should be registered in the case report form (CRF).

All SAEs should be reported to Novartis on specific SAE forms within 24 hours of learning of its occurrence to:

Clinical Safety Desk Fax:

To be answered: Has there been any occurrences of (clinically relevant) AEs since the 3-year follow-up visit i.e. from the 3-year follow-up visit to the 5 to 7-year follow-up visit.

The total number of each AE/SAE should be recorded, i.e. one patient may have experienced several AEs. Further details regarding collection and handling of AEs/SAEs are provided in Appendix 1.

• **Table 2 Selected Adverse Events – Main Categories**

Adverse Event	3 years to 5/7 years	
	AE	SAE
Infection		
Pneumonia		
Herpes Zoster		
Herpes simplex		
Sepsis		
Cancer		
Squamous cell carcinoma		
Basal cell carcinoma		
Other skin cancer		
PTLD		
Solid tumor		
Bone marrow toxicity		
Thrombocytopenia (<100000/ μ L)		
Leucopenia (<3500/ μ L)		
Anemia (<10 g/dL)		
Tromboembolic event		
DVT		
Pulmonary emboli		
Stroke/TIA		
Gastrointestinal system		
Diarrhea		
Constipation		
Pain		
Skin		
Rash		
Acne		
Hirsutism		
Cardiac		
Cellular rejection (grade)		
Humoral rejection		
LV dysfunction (EF<30%, or 25%↓)		
Arrhythmias (clinically significant, requiring treatment)		
PCI		
Myocardial infarction		

Adverse Event	3 years to 5/7 years	
	AE	SAE
Renal		
Proteinuria (albumin/creatinine >100)		
Hyperuricemia		
Peripheral oedema		
Gingival hyperplasia		
Other		

4.5.3 Instructions for collecting and reporting Adverse Events and Serious Adverse Events

The purpose of this instruction is to guide how to collect and handle the side effects from a practical point of view.

- When the patient comes to the clinic visit, ask him/her if there have been any adverse events (clinically relevant) since the 3-year follow-up visit (i.e. between the 3-year follow-up visit and the 5 to 7-year follow-up visit).
- Record serious and non-serious AEs and the total number of each event in the CRF (each patient might have experienced several events).
- Check the adverse events/serious adverse events against medical records in order to source verify the events.
- The serious adverse events must be reported to Novartis within 24 hours of learning of its occurrence.
- State in the medical record for the study visit:
 - that the patient has been asked for clinically relevant adverse events
 - the events reported by the patient
 - refer to where in the medical record the different adverse events can be found (e.g. by date).
- If the reported adverse events cannot be verified in medical record/any other source document the patient should be asked if he/she has been in contact with a doctor/hospital and/or received treatment due to the event and attempt to retrieve this information from the treating physician/hospital. It is important to make an effort to find the medical records/source documents and to document this for the study visit in the medical records.
- As for the original study (CRAD001NO02, EudraCT number 2009-013074-41), everolimus (Certican®) is defined as the study drug. If the SAE is not previously documented in the IB or Package Insert for (new occurrence) and is thought to be related to the study drug a Drug Safety and Epidemiology Department associate may urgently require further information from the investigator for health authority reporting. Novartis may need to issue an Investigator Notification to inform all investigators involved in any study with the same study treatment that this SAE has been reported. Suspected Unexpected Serious Adverse Reactions will be collected and reported to the competent authorities and relevant ethics committees in accordance with EU Guidance 2011/C 172/01 or as per national regulatory requirements in participating countries.

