This protocol is written to describe the procedures for a single 5, 6 or 7 year follow-up control visit of patients that participated in the 12-month SCHEDULE-study and the following 3-year follow-up examination/visit. The aim of this 5 to 7-year follow-up visit is to examine the effect of long term treatment, i.e. 5, 6 or 7 years, with early initiation of everolimus (Certican®) and early elimination of cyclosporine (CsA), compared to standard immunosuppressive regimen including CsA, on renal and heart function. During the time period of this follow-up examinations this visit will be performed as part of a routine annual visit 5, 6 or 7 years since transplantation (and inclusion in the original SCHEDULE study).

PROTOCOL FOR THE 5 TO 7-YEAR FOLLOW-UP EXAMINATION

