6.2 Blind Review

This is an open study, however before data base lock the final decisions of patients to be included in study populations, as defined in Section 5 will be made and documented in the Pre-Analysis Review Form.

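### Protocol 4.5.3 has no step for finding Table 2 events that the patient does not mention, although 4.5.2 requires all of them to be registered

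*Protocol*

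**What the plan says.** Protocol 4.5.2 sets the requirement. Table 2 lists the events of interest, and "Any of these AEs that have occurred during the time between the 3-year follow-up visit and the 5 to 7-year follow-up visit" is to be registered in the case report form, with a count for each event. The duty is not limited to events that the patient reports.

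Protocol 4.5.3 gives the procedure. At the visit the site is to "ask him/her if there have been any adverse events (clinically relevant) since the 3-year follow-up visit", record serious and non-serious events, and then "Check the adverse events/serious adverse events against medical records in order to source verify the events". Outside records are pursued in one situation: "If the reported adverse events cannot be verified in medical record/any other source document the patient should be asked" about contact with a doctor or hospital, and the site then tries to obtain the documents. The visit note must show that the question was put, what the patient reported and where each event can be found in the record.

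The follow-up consists of "a single 5, 6 or 7 year follow-up control visit of patients". SAP 6.2 describes the trial as open: "This is an open study, however before data base lock the final decisions of patients to be included in study populations" are settled. The number of adverse and serious adverse events is a secondary endpoint in Protocol 2 and the safety endpoint in SAP 3.3.

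**The concern.** The requirement in 4.5.2 is complete capture, but the method in 4.5.3 corrects errors in one direction only. A reported event that did not happen can be removed by checking the record. An event that happened but was not reported has no stated route into the case report form.

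This matters because several Table 2 rows are not things a patient would normally know. Examples are "Thrombocytopenia (<100000" per microlitre) and "Anemia (<10 g/dL"). Leucopenia, proteinuria, hyperuricemia and a fall in ejection fraction are of the same kind.

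At stake is the completeness of a listed endpoint that readers will compare between arms. Patients and staff know the treatment, and Protocol 1.1 itself names different expected harms for the two drug classes. What is asked and what is remembered could therefore differ by arm.

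**Working it through.** The documents give no event rate, capture rate or sample size for this follow-up (SAP 4.2 calls the last not applicable), so there is no planned figure to reproduce. The check is a comparison of sections, with a labelled illustration at the end.

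**Look-back window.** Nominal visit year minus 3: 5 − 3 = 2, 6 − 3 = 3 and 7 − 3 = 4 years.

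**Patients affected.** At most the 102 of 115 who attended the 3-year visit (102/115 = 88.7%).

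**Table 2 rows that depend on a test, and the routes by which they can be found.**

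| Rows | Found at the visit by | Stated route for the interval |
|---|---|---|
| Thrombocytopenia, leucopenia, anemia | Hematology (4.3.8) | None beyond the patient question |
| Proteinuria, hyperuricemia | Albumin/creatinine ratio, uric acid (4.3.3, 4.3.8) | None beyond the patient question |
| LV dysfunction | Echocardiography with LVEF (4.3.4) | None beyond the patient question |
| Cellular and humoral rejection | Not applicable | Separate item since year 3 (4.3.7) |

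This leaves 3 + 2 + 1 = 6 test-defined rows that are covered on the visit day but have no stated search between visits. Clinical rows such as infections or gastrointestinal events rest on recall, supported by verification.

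**Does another section fill the interval?**
- SAP 6.3.11 summarises laboratory values at scheduled visits, with no time point between the 3-year visit and the 5 to 7-year visit.
- Protocol 4.3.2 collects starts and stops of immunosuppression with reasons. These may prompt a site to notice an event but are not a search for events.
- Protocol 5 requires full verification of serious event documentation and of recorded safety data. It describes this as agreement between source and case report form, not as a search for unentered non-serious events.
- Protocol 4.5.2 refers to an Appendix 1 for further detail, which is not in the text available. The SAP's own Appendix 1 is a list of tables and listings and does not address collection.

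**Illustration (all rates assumed).** Observed proportion = true proportion × share captured.
- Equal capture of 60% to 90% in both arms: a true difference of 20 points appears as 0.6 × 20 = 12 to 0.9 × 20 = 18 points.
- Equal true proportions of 20% to 50%, with capture differing by 10 to 20 points: the false difference runs from 0.20 × 0.10 = 2 points to 0.50 × 0.20 = 10 points.
- Equal true proportions and equal capture: no false difference.

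These figures show how the mechanism works. They do not estimate what will happen in this trial.

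**The case against.** The strongest reply is that 4.5.2 already obliges sites to register every Table 2 event, that 4.5.3 is practical guidance which does not narrow that duty, and that Appendix 1, the case report form and the monitoring plan may contain the missing step. Visit-day tests cover all five laboratory rows, echocardiography covers ejection fraction, and rejections are collected separately. SAP 6.3.10 plans descriptive tables and counts a preferred term once per patient, so a missed repeat event would not change that count.

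Most of this stands as a limit on the point. A reader might infer that unreported and laboratory-defined events will be missed. The documents do not support that: abnormalities present at the visit should be detected, and some sites may search records because of 4.5.2. A reader might also infer that no record search is planned anywhere. That cannot be said while Appendix 1 is unseen. Nor do the documents give a direction or size for any difference between arms.

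The reply does not remove the gap in 4.5.3 itself. A site that follows its steps exactly can miss a low platelet count that resolved at year 4, or an infection the patient has forgotten. If Appendix 1 contains a search, 4.5.3 should point to it.

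**Conclusion.** The point holds as a mismatch between two sections: 4.5.2 asks for all Table 2 events over 2 to 4 years, and the steps in 4.5.3 lead from the patient's answer to the record but not back. Transient laboratory or ventricular-function abnormalities between visits, and clinical events the patient does not recall, may be missed. Because the study is open, the loss may differ by arm.

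The size of the undercount is unknown. No hypothesis test is planned on these data, and the mGFR analysis is not affected. The consequence is limited to how far the event counts can be trusted as complete and comparable. The conclusion rests on reading the record check in 4.5.3 as verification of events already named, which is what its wording says, and is subject to whatever Appendix 1 contains.

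**What to change.** Reword 4.5.3 so that, for every patient and in the same way in both arms, the site:

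1. reviews the medical record and the available laboratory, echocardiography and biopsy results since the 3-year visit against each row of Table 2, using the limits printed there;
2. enters every qualifying event, whether or not the patient mentions it;
3. then asks the patient about events treated elsewhere, keeping the existing steps for tracing them;
4. records the date of each event and its source (record, patient or both).

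If Appendix 1 already describes such a review, a cross-reference from 4.5.3 and the source field would be enough.

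The cost is a wording change, a small addition to the case report form and site time to go through 2 to 4 years of records for up to 102 patients. No new visit, procedure or staff is needed. One limitation remains: interim laboratory events can be found only where tests were done, so their number will depend on how often each patient was tested. If testing frequency differs between arms, so may the counts, and this should be stated wherever the arms are compared.

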4.5.4 Pregnancy

To ensure patient safety, each pregnancy occurring while the patient is on study treatment must be reported to Novartis within 24 hours of learning of its occurrence. The pregnancy should be followed up to determine outcome, including spontaneous or voluntary termination, details of the birth, and the presence or absence of any birth defects, congenital abnormalities, or maternal and/or newborn complications.

Pregnancy should be recorded on the Pharmacovigilance Pregnancy Form and reported by the investigator to the local Novartis Drug Safety and Epidemiology Department.

5. SITE MONITORING

Formal site monitoring will be performed as described in the Monitoring Plan for this study. Novartis designated CRO will assure compliance monitoring

During the study, the field monitor will visit the site regularly to check the completeness of patient records, the accuracy of entries on the paper CRFs, the adherence to the protocol and to Good Clinical Practice and the progress of enrollment. Key trial personnel must be available to assist the field monitor during these visits.

The investigator must maintain source documents for each patient in the study, consisting of case and visit notes (hospital or clinic medical records) containing medical information, laboratory data, electrocardiograms, and the results of any other tests or assessments. All information on CRFs must be traceable to these source documents in the patient's file which will be documented as being the source data. The investigator must also keep a copy of the signed informed consent form.

The investigator must give the monitor access to all relevant source documents to confirm their consistency with the CRF entries. Novartis monitoring standards require full verification for the presence of informed consent, adherence to the inclusion/exclusion criteria, documentation of SAEs, and the recording of data that will be used for all primary and safety variables. Additional checks of the consistency of the source data with the CRFs are performed according to the study-specific monitoring plan. No information in source documents about the identity of the subjects will be disclosed.

Access to source documents by auditors and regulatory inspectors will be granted.

6. ETHICS AND GOOD CLINICAL PRACTICE

This study was planned and shall be performed according to the principles of Good Clinical Practice, the declaration of Helsinki, and national laws and regulations about clinical studies. The study will not start without written Institutional Review Board/Independent Ethics Committee/Research Ethics Board approval and the written informed consent of the patient.

[figure not shown]

7.4	US Archival Listings (Appendix 16.4 according to ICH E3).....	18

ABBREVIATIONS

AE	Adverse Event
ANCOVA	Analysis of Covariance
BDI	Beck Depression Inventory
BiVad	Biventricular Assist Device
BMI	Body Mass Index
CAV	Cardiac Allograft Vasculopathy
CI	Confidence Interval
CRF	Case Report Form
CsA	Cyclosporine
CSP	Clinical Study Protocol
ECG	Electrocardiogram
ECMO	Extra Corporal Membrane Oxygenation
EQ-5D	Euro Quality of Life 5D
FF	Fractional shortening
IMP	Investigational Medicinal Product
ITT	Intention-to-Treat
IVUS	Intravascular Ultrasound
LOCF	Last Observation Carried Forward
LVAD	Left Ventricular Assist Device
LVEDD	Left Ventricular End Diastolic Dimension
LVEF	Left Ventricular Ejection Fraction
LVESD	Left Ventricular End Systolic Dimension
MedDRA	Medical Dictionary for Regulatory Activities
MDRD	Modification of Diet in Renal Disease Study Group
mGFR	measured Glomerular Filtration Rate
MMF	Mycophenolate Mofetil
MMRM	Mixed Model Repeated Measures
PPS	Per Protocol Set
SAE	Serious Adverse Event
SAP	Statistical Analysis Plan
SF-36	Short Form 36
SOC	System Organ Class
VAS	Visual Analogue Scale
WHO	World Health Organization

1 INTRODUCTION

This Statistical Analysis Plan (SAP) is based on Clinical Study Protocol (CSP) final version 2.0 DK, dated 07-Jul-2016 including Amendments No. 1, dated 27-Jun-2016 and Updates to Section 4.5 as requested by the Danish Health Authority. The CSP describes the procedures for a single 5, 6 or 7 year follow-up control visit of patients that participated in the 12-month SCHEDULE-study and the following 3-year follow-up examination/visit.

2 STUDY OBJECTIVES

Purpose

To evaluate, in *de novo* heart transplant recipients, whether early initiation of everolimus and early elimination of cyclosporine (CsA), compared to standard immunosuppressive regimen including CsA can improve long-term renal function and slow down the progression of Cardiac Allograft Vasculopathy (CAV).

Aim

The major aim of this extension study is to evaluate the long-term (i.e. 5 to 7 years) effect of early initiation of everolimus and early elimination of CsA compared to standard immunosuppressive regimen including CsA on primary and secondary endpoints investigated in the SCHEDULE main study.

3 EFFICACY AND SAFETY ENDPOINTS

3.1 Primary Efficacy Endpoint

The primary endpoint is renal function as assessed by measured glomerular filtration rate (mGFR) 5-7 years after randomization.

3.2 Secondary Efficacy Endpoints

[figure not shown]
- Progression of CAV by Intravascular Ultrasound (IVUS) analysis
- Myocardial structure and function by echocardiography assessment
 - Left Ventricular End Diastolic Dimension (LVEDD) (cm)
 - Left Ventricular End Systolic Dimension (LVESD) (cm)
 - Left Ventricular Ejection Fraction (LVEF) (%)
 - Fractional shortening (FF) %
- The variables will be presented for week 2, baseline, month 12, 3-years follow-up and 5-7-years follow-up visit.
- Quality of life will be presented for pre-transplantation, month 12, 3-years follow-up, 5-7-years follow-up visit and change from pre-transplantation
 - Short Form 36 version 2 (SF-36): consists of 36 questions of health-related quality which each can take one of five responses. The 36 questions are divided

[figure not shown]
in eight dimensions; Physical Functioning, Role Physical , Bodily Pain, General Health, Vitality, Social Functioning, Role Emotional and Mental Health. QualityMetric Health Outcomes™ Scoring Software, Based on 1998 US Norms, will be used for the calculations of the eight dimensions plus Physical Health Summary and Mental Health Summary.

- Euro Quality of Life 5D (EQ-5D): is a descriptive system of healthrelated quality of life states consisting of five dimensions (mobility, self-care, usual activities, pain/discomfort and anxiety/depression) each of which can be assessed as one of three levels of severity (no problems/some or moderate problems/extreme problems). A Visual Analogue Scale (VAS)-scale is also included in the EQ-5D questionnaire. An EQ-5D index will be calculated based on the United Kingdom TTO N3 value set. The algorithm for the EQ-5D index is received from EuroQoL Research Foundation.
- Beck Depression Inventory (BDI): the form consists of 21 questions to measure the intensity, severity, and depth of depression. The total score per patient and assessment will be between 0 to 63. The total score will be classified in two different ways according to investigator:
 - 0-9 Normal
 - 10-15 Mild
 - 16-23 Moderate
 - 24-63 Severe
 - 0-9 Normal
 - 10-15 Mild
 - 16-63 Moderate/Severe

3.3 Safety Endpoints

Number of Adverse Events (AEs)/Serious Adverse Events (SAEs).

4 OVERALL STUDY DESIGN

4.1 Overview of Study Design

The 12-months SCHEDULE main study was a prospective, multi-center, randomized, controlled, parallel group, open label study in de novo heart transplant recipients. The study consisted of two study periods, period 1 (HTx to week 7-11) and period 2 (week 7-11 to Month 12). Patients fulfilling the inclusion and exclusion criteria were randomized to one of two treatment groups: (i) conventional treatment with CsA, mycophenolate mofetil (MMF), and corticosteroids (Group A), or (ii) low-dose CsA, everolimus, MMF, and corticosteroids (Group B). After period 1, CsA was discontinued in Group B (experimental set-up with off-label use of everolimus), while the standard triple-drug immunosuppressive regimen was maintained in Group A.

In the 12-month SCHEDULE-study, 115 patients were randomized and treated. The patients were recruited from six transplant centres in Norway, Sweden and Denmark. The main study was followed by a 3-year follow-up visit in which 102 of the 115 patients participated. This 5 to 7-year follow-up visit is a further longtime follow-up examination of the patients participating in the SCHEDULE main study and the 3-year follow-up visit.

After completion of the 12-month SCHEDULE study, some patients have continued on the same immunosuppression and some of the patients have switched to alternative immunosuppressive treatment.

Patients who have participated in the 12-month SCHEDULE study and the 3-year follow-up visit and who are coming for an annual 5 to 7-year follow-up visit after randomization will be asked to participate.

The patients will be allocated to the same randomization group as in the 12-month SCHEDULE study for which stratified randomization and the following four strata were applied:

- mGFR ≤60 mL/min before transplantation AND mechanical assist device, Left Ventricular Assist Device (LVAD), Biventricular Assist Device (BiVad) or Extra Corporal Membrane Oxygenation (ECMO)
- mGFR ≤60 mL /min before transplantation AND no mechanical assist device
- mGFR >60 mL /min before transplantation AND mechanical assist device
- mGFR >60 mL /min before transplantation AND no mechanical assist device

